At 1000 am on Day 2 and Day 3, the BPI and POS will be completed. If there is a reduction in pain scores, the BPI and POS will continue to be completed on Day 7, 14 and 21 post each infusion, or until the worst pain score on the BPI #3 has returned to baseline. If there is no change, the questionnaires for Day 7 will be completed and the patient will be scheduled for the next follow up visit and treatment within a minimum of 48 hours and maximum of three weeks of the pain returning to baseline. The Medication Use Log is to be completed daily, and the Adverse Events Log completed if an adverse event occurs. Telephone contact will be made at a minimum twice a week until the pain is back to the pre-treatment level by the research nurse or physician and to adjust medications if necessary, and, once pain returned to baseline, once weekly telephone contact will be done til the 2nd treatment visit to review any condition or medication changes. Subjects will also be encouraged to call the physician at any time if they experience any adverse event or to report return to baseline pain score.

Once the worst pain score on the BPI (question #3) has returned to baseline and at least 48 hours have elapsed, the second treatment will be arranged. If there is a response the patient will continue with diaries and questionnaires weekly until the BPI score returns to baseline

Second Treatment Visit

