This will be arranged within a minimum of 48 hours and maximum of three weeks of the pain returning to baseline but will be no earlier than 48 hours after the 1st treatment. The baseline weight will be used to determine the dose for the second treatment. At 1000 am on Day 2 and Day 3 post second treatment, the BPI and POS will be completed. If there is a reduction in pain scores, the BPI and POS will continue to be completed on Day 7, 14 and 21 post each infusion, or until the worst pain score on the BPI #3 has returned to baseline, at which time the end of study visit will be arranged within a minimum of 48 hours and a maximum of three weeks of the pain returning to baseline. If there is no change, the questionnaires for Day 7 will be completed and the patient will be scheduled for the end of study visit within a minimum of 48 hours and maximum of three weeks of the pain returning to baseline. The Medication Use Log is to be completed daily, and the Adverse Events Log completed if an adverse event occurs. Telephone contact will be made at a minimum twice a week until the pain is back to the pre-treatment level. Subjects will also be encouraged to call the physician at any time if they experience any adverse event or to report return to baseline pain score.

Final Visit Post Second Infusion (once the worst pain score on the BPI (question #3) has returned to baseline by phone assessment and at least 48 hours or a maximum of three weeks of the pain returning to baseline., At this visit subjects will again complete the Brief Pain Inventory and POS and their Medication Use Log and Adverse Events Log will be reviewed. This will be the end of the study.

Outcome measures:

Primary:

The primary outcomes measure is a binary variable indicating whether lidocaine caused a reduction in cancer pain within 48 hours of infusion and lasting a minimum of 7 days. Lidocaine will be considered to have caused reduction in cancer pain if the subject had either one of the following episodes lasting a minimum of 7 days:

- 1) A 2-point reduction in severity of pain as assessed by the worst pain score in the last 24 hours (question 3) of the Brief Pain Inventory – Short Form (BPI), compared to the BPI pain score at baseline.

Or:

- 2) ≥30% reduction in 24-hour opioid dose.

The duration of the pain reduction is measured by weekly BPI pain scores.,

Secondary:

- 1) Incidence and severity of adverse events.

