- 2) Effect of Lidocaine infusion on QOL parameters as measured by the Patient Outcome Scale (POS) Questionnaire
- 3) Duration of response to lidocaine infusion.

Notes on Outcome Measures

The BPI refers to “worst pain over the last 24 hours” rated between 0 and 10, and a 2 points difference has been determined in multiple studies to be clinically useful. Based on our experience with lidocaine infusions already we know that a response to lidocaine occurs within the first 3 days (actually usually within the first 24 hours), so the daily BPI for the first 3 days will capture whether or not a clinically significant improvement in pain has been achieved.

Because some patients may accept similar levels of pain but reduce their opioid analgesics significantly, with consequent reduction in side-effects, the 30% reduction in analgesic use is also included as indicative of a positive response, to ensure that clinically meaningful benefits are not missed by relying just on the pain scores.

For this study significant toxicity is considered as any adverse event which either leads to the infusion being terminated, or which leads to medical intervention, such as prescribing of another medication or equivalent treatment.

The Patient Outcome Scale (POS) is a QOL tool used routinely in the BCCA PSMPC clinics that addresses physical, psychological, spiritual, practical, psychosocial and emotional concerns and consists of 12 questions in 9 domains: pain, other symptoms, anxiety, information, support, depression, self-worth, wasted time and personal affairs. It was used in the Subcutaneous Lidocaine Feasibility Study.

The duration of response is a descriptive outcome which will be determined by the time to return of the BPI question #3 worst pain in 24 hours pain rating to the same as at that provided on the morning of the infusion, before the infusion started. The duration of benefit will be reported in descriptive terms only and is not an endpoint which will be subject to statistical analysis. This data will be useful for planning subsequent clinical implementation, if the study shows the treatment to be effective.

Schedule of Assessments:

Baseline:

Age, gender, weight, history and physical, cancer diagnosis, Palliative Performance Scale (PPS), and Edmonton Classification System for Cancer Pain (ECS-CP), physician assessment of cause(s) of pain(s), medication and allergy history, blood pressure, pulse rate and ECG, BPI, POS and blood draw if needed.

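### Duration of response is timed on worst pain alone, so a patient who responds by cutting opioid with unchanged pain has a zero or undefined duration

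*Combined protocol and SAP*

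**What the plan says.** The primary outcome (Outcome measures, Primary) is binary. It is met by an episode of at least 7 days of either a 2-point fall in BPI question 3 (worst pain) or at least a "30% reduction in 24-hour opioid dose". Study Objectives words the composite more tightly: a pain reduction with opioid use not increased, or the opioid reduction with no decrease in pain. Notes on Outcome Measures explains that the opioid limb is there for patients who tolerate about the same pain on less opioid.

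The third secondary outcome is "Duration of response to lidocaine infusion". Its definition, in Notes on Outcome Measures, reads: "The duration of response is a descriptive outcome which will be determined by the time to return of the BPI question #3 worst pain", taken to the "pain rating to the same as at that provided on the morning of the infusion, before the infusion started". It has no opioid component and no 2-point threshold. The section adds: "The duration of benefit will be reported in descriptive terms only and is not an endpoint which will be subject to statistical analysis". It gives the intended use as: "This data will be useful for planning subsequent clinical implementation, if the study shows the treatment to be effective".

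On follow-up, Between Visits says: "If there is a reduction in pain scores, the BPI and POS will continue to be completed on Day 7, 14 and 21", or until worst pain is back to baseline. Second Treatment Visit repeats this. Schedule of Assessments ties the same questionnaires to a response to treatment, but also stops them once question 3 is back to baseline.

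**The concern.** Response has two limbs and duration of response has one. A patient who responds through the opioid limb with flat pain is at the baseline score throughout, so the duration rule has nothing to time. The same patient's primary outcome requires at least 7 days of benefit. The two results for one patient then disagree, and the disagreement comes from the stated rule.

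Duration is a stated secondary objective and is meant to inform how the treatment is put into practice. If opioid-limb responders enter the summary as zeros, the reported duration is pulled down. If they are left out, the figure describes only part of the responders. The same reliance on worst pain governs who completes the Day 14 and Day 21 questionnaires, and missing BPI and POS forms cannot be recovered afterwards.

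A lesser matter concerns pain-limb responders. The clock runs until worst pain is fully back to baseline, which may be later than the loss of the 2-point difference that the plan calls clinically useful.

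**Working it through.** **Plan's own figure.** The plan states no figure for duration. Its power figure was checked only to confirm that duration plays no part in it. With 30% placebo response, a 20-point difference and 0.01% of lidocaine non-responders responding to placebo (Statistical Considerations):

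- p01 = 0.50 × 0.0001 = 0.00005
- p10 = 0.50 − 0.30 + 0.00005 = 0.20005
- Exact one-sided McNemar power with 40 patients: 83.8%, at 0.025 and also at 0.02347 (stated: 84%)
- Drop-out: 40 / (1 − 0.20) = 50

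**Applying the duration rule.** The score paths below are assumptions, with pre-infusion worst pain 8 and BPI on Days 2, 3, 7, 14 and 21. In the opioid-limb rows, 24-hour opioid is 40% lower through Day 14 and the reduction is gone at Day 21. In the pain-limb rows, opioid is unchanged.

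| Assumed patient | Worst pain, Days 2, 3, 7, 14, 21 | Plan's rule | First assessment with the response limb lost |
|---|---|---|---|
| Opioid limb, flat pain | 8, 8, 8, 8, 8 | 0 or undefined | Day 21 |
| Opioid limb, 1-point fall | 7, 7, 7, 8, 8 | Day 14 | Day 21 |
| Pain limb, gradual fade | 4, 5, 6, 7, 8 | Day 21 | Day 14 |
| Pain limb, 1-point plateau | 5, 5, 6, 7, 7 | after Day 21 | Day 14 |
| Pain limb, abrupt return | 4, 4, 5, 8, 8 | Day 14 | Day 14 |

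The second row is possible only under the looser either-limb wording of the primary outcome. Under the Study Objectives wording, opioid-limb responders have no fall in pain and all resemble the first row.

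**Size for pain-limb responders.** Assume a fall of d points that returns linearly over T days. The 2-point benefit ends at T(1 − 2/d). For a patient who just keeps 2 points to Day 7, T = 7 / (1 − 2/d):

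- d = 3: T = 21.0 days
- d = 4: T = 14.0 days
- d = 5: T = 11.7 days

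In continuous time the ratios to 7 days are 3.0, 2.0 and 1.7. After Day 3, however, scores are seen only on Days 7, 14 and 21. In all three cases the loss of 2 points is first seen on Day 14. Full return is first seen on Days 21, 14 and 14. The recorded ratios are 21/14 = 1.5, 14/14 = 1.0 and 14/14 = 1.0.

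**Questionnaires.** Under Between Visits and Second Treatment Visit, a patient with no change in pain completes Day 7 and stops. Under Schedule of Assessments, an opioid-limb responder counts as a responder, but the stopping condition (question 3 at baseline) is already met if pain is flat. Either way, up to two sets per period, Days 14 and 21, can be missing. The Medication Use Log is completed daily regardless.

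**The case against.** The strongest defence is that time to return to the pre-infusion score is a fully specified measure of how long any benefit lasts, and the same event already times the second infusion and the final visit. For pain-limb responders this stands. The value is correct for what it measures, so what remains is a labelling point.

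Three stronger readings are tempting, and the documents do not support them:

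- **That every opioid-limb responder is recorded as zero.** The plan does not say how a patient whose score never left baseline is recorded, so undefined is as possible as zero. Under the looser wording, a patient with a 1-point fall has a positive duration.
- **That a pain-limb patient who fades to 1 point below baseline stops being a responder and so contradicts the primary result.** The primary outcome is binary and met by 7 days of benefit. A later fade does not undo it.
- **That useful duration is overstated 3.0-, 2.0- or 1.7-fold.** Those ratios need continuous observation. On the plan's assessment days the same cases give 1.5, 1.0 and 1.0. Longer responses could give larger ratios, and an abrupt return gives no difference.

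It is also fair to say that flat-pain opioid responders may be few. Between Visits allows long-acting opioid to be reduced only when the patient feels pain control has improved sufficiently. The documents give no expected number. But Study Objectives and Notes on Outcome Measures both foresee such patients, so the case cannot be dismissed.

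**Conclusion.** The concern holds for the opioid limb. Response includes an opioid reduction, duration of response is timed on worst pain alone, and no other section supplies an opioid-limb rule. A flat-pain opioid responder has a zero or undefined duration against at least 7 days in the primary outcome, and later BPI and POS data for that patient can be lost. This follows from the wording and needs no numerical assumption. How many patients it affects is unknown.

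For pain-limb responders the rule times full return to baseline, which can exceed the time the 2-point benefit is held if pain fades gradually. The gap depends on the fade and the visit days: Day 21 against Day 14 for a 3-point fall under the linear assumption, and none for 4- or 5-point falls in the same setting.

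Severity is minor. A reader might infer that the trial's main conclusion is at risk, but duration is descriptive and untested, and enters neither the McNemar test, the alpha split nor the sample size.

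**What to change.** Define duration of response as the time to the first assessment at which neither response limb holds. The limbs are:

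- worst pain at least 2 points below that period's pre-infusion score, with no increase in 24-hour opioid; or
- 24-hour opioid at least 30% below baseline, from the daily Medication Use Log.

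The no-increase condition comes from Study Objectives. Without it, duration could be credited to pain held down by extra opioid. Censor at the last assessment or at the second infusion, and state which pre-infusion log days supply the opioid baseline.

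Report time to full return of question 3 to baseline separately, under that name. Leave its use as the scheduling trigger unchanged. Reword Between Visits, Second Treatment Visit and Schedule of Assessments so that Day 14 and Day 21 questionnaires continue for responders on either limb.

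The cost is a wording change and up to two extra short questionnaire sets per period for some opioid-limb responders. The opioid data are already collected daily. The questionnaire change has to be made before data collection; the duration definition can be applied to the existing logs.

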This study's primary objective is to test the hypothesis that a single infusion of subcutaneous lidocaine can cause a clinically useful reduction in cancer pain within 48 hours of infusion and lasting a minimum of 7 days. A clinically useful reduction in pain is defined by either a 2-point reduction (on a 0-10 scale) in the worst pain experienced over a 24-hour period, or a $\geq 30\%$ reduction in 24-hour opioid requirement. We will use a composite endpoint of reduction in pain without increase in 24-hr opioid requirement or no decrease in pain with a $\geq 30\%$ reduction in 24-hour opioid requirement.

The secondary objectives are 1) to determine whether any significant toxicities occur as a result of the infusion. For this study significant toxicity is considered as any adverse event which either leads to the infusion being terminated, or which leads to medical intervention, such as prescribing of another medication or equivalent treatment, 2) to determine the effect of Lidocaine infusion on QOL parameters as measured by the Patient Outcome Scale (POS) Questionnaire and 3) to determine the duration of response to lidocaine infusion.

Eligibility criteria:

Male or female patients 18 years of age or older
In or outpatients referred to the BCCA PSMPC Clinics with a diagnosis of cancer
Subjects must have somatic, visceral or neuropathic pain related to cancer
Pain intensity, measured by a worst pain score over the last 72 hours of ≥ 4 on a 0-10 numerical rating scale
Must have tried at least one opioid medication without adequate response or with significant side-effects for at least one week
For those with neuropathic pain, must have also tried at least one adjuvant analgesic, such as a tricyclic (unless contraindicated) or an anticonvulsant without adequate response or with significant side-effects for at least one week
Life expectancy of > 3 months
Must be able to communicate symptoms indicating potential toxicity of Lidocaine
Must have a competent caregiver in the home overnight after each infusion
Must be willing to remain within 30 minutes of the Cancer Centre during each infusion

Exclusion criteria:

Clinically significant cardiac disease, i.e, cardiac failure, atrial fibrillation with slow ventricular rate (<60), any degree of heart block

New analgesic treatment initiated in time frame which might have effect within one week of study drug.

Hyper or hypokalemia.

Liver failure (bilirubin ≥ 25 μ mol/L).

Renal failure (eGFR <50% of normal)

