Final Visit: (post 2nd infusion, once the worst pain score on the BPI (question #3) has returned to baseline by phone assessment and minimum 48 hours and a maximum of three weeks since the return to baseline., At the final visit, the ,BPI, POS, Medication Use Log. Adverse Events Log and PPS will be reviewed

A positive response re: pain relief would be defined as any of the following:

- A 2-point reduction in worst pain intensity (#3 on the BPI) within 48 hours of infusion and lasting a minimum of 7 days
- Reduction in analgesic dose by greater or equal to 30% will also be considered an indicator of positive response.

Statistical Considerations: **Objective**

To compute the power and sample size calculation for the study

Assumptions

- Probability of response in the placebo group = 30%
- There is no carry-over effect, no period effect and no sequence effect in the study

- 0.01% of the patients who did not respond to the lidocaine will respond to the placebo

Null Hypothesis: There is no difference between a single infusion of subcutaneous lidocaine and the placebo

Alternative Hypothesis: A single infusion of subcutaneous lidocaine can cause a reduction in cancer pain

Sample Size / Interim Analysis

A sample size of 40 patients achieves 84% power to detect a 20% difference at a 2.5% significance level using a one-sided McNemar's Test, under the assumptions that 30% of the patients respond to the placebo and 0.01% of the patients who do not respond to the lidocaine will respond to the placebo. This sample size is increased to 50 patients to account for a 20% drop-out rate. This drop-out rate is based on our experience accruing similar patients to studies. The sample size methodology is based on the methodology described in Lachenbruch 1992.

We have demonstrated in the completed Feasibility Study for a Randomized Double Blind Placebo Controlled Crossover Trial of the Use of Subcutaneous Lidocaine Infusion for Chronic Cancer-related Pain that recruitment to such a study is feasible, and that we should expect this study to take 6 months for accrual.

An interim analysis will be carried out after 20 patients have completed the study to allow the trial to be stopped early for demonstrated efficacy. One-sided McNemar's tests will be carried out to test whether a single infusion of subcutaneous lidocaine will cause a reduction in cancer pain for both the interim and final analyses at the p-values of 0.00153 and 0.02347 respectively.

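### Duration of response is named for lidocaine only and kept out of statistical analysis, so no comparison with placebo is planned although both infusions supply the data

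*Combined protocol and SAP*

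**What the plan says.** Under Study Objectives, the third secondary objective is "to determine the duration of response to lidocaine infusion". The secondary list under Outcome measures repeats it as "Duration of response to lidocaine infusion". Neither mentions placebo.

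The Notes on Outcome Measures give the measuring rule: the time for BPI question 3 to return from its post-infusion level to a "pain rating to the same as at that provided on the morning of the infusion, before the infusion started". They then set its status: "The duration of benefit will be reported in descriptive terms only and is not an endpoint which will be subject to statistical analysis". They also state its purpose: "This data will be useful for planning subsequent clinical implementation, if the study shows the treatment to be effective".

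Data collection does not differ by treatment. Between Visits and Second Treatment Visit both say that, where pain scores fall, "the BPI and POS will continue to be completed on Day 7, 14 and 21 post each infusion", or until worst pain is back at baseline. Patients with no change still complete the Day 7 forms. The Schedule of Assessments applies the same rule after each infusion.

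**The concern.** The Clinical Experience section already reports uncontrolled durations after subcutaneous lidocaine (15 to 21 days in most of that clinic's patients), and the protocol goes on to argue that a randomised placebo-controlled trial is needed. On duration, the plan as written specifies another figure with no comparator, from a trial that has one. Pain in these patients can fall and return after either infusion, through placebo response, fluctuation, or regression from a high score on the infusion morning. Time to return to baseline after lidocaine includes all of that.

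At stake is the interpretation of one secondary result. Someone deciding how often to offer the infusion would see how long relief lasted, with no planned estimate of how much longer it lasted than after placebo.

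**Working it through.** **1. The plan's own figure.** No figure is stated for duration. The only one that can be reproduced is the primary endpoint's power, under Sample Size / Interim Analysis. Inputs: placebo response 0.30; lidocaine response 0.30 + 0.20 = 0.50; and the assumption that "0.01% of the patients who did not respond to the lidocaine will respond to the placebo".

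- Placebo only: 0.0001 × 0.50 = 0.00005
- Both: 0.30 − 0.00005 = 0.29995
- Lidocaine only: 0.50 − 0.29995 = 0.20005

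The exact one-sided McNemar test with 40 patients at 0.025 has power 83.8%, against the stated 84%. The figure reproduces, and this point does not affect it.

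**2. What is planned for each outcome.**

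| | Primary response | Duration (secondary 3) |
|---|---|---|
| Wording | names lidocaine | names lidocaine |
| Measured after both infusions | yes | yes |
| Comparison with placebo | McNemar test | none; statistical analysis excluded |
| Content | yes/no, at least 7 days | time to return to pre-infusion score |

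The lidocaine-only label is common to both. What separates them is that the Statistical Considerations supply a placebo comparison for the primary, while the notes rule out analysis for duration.

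**3. Can the attributable share be calculated?** Suppose mean durations among responders are L after lidocaine and P after placebo, with response rates of 0.50 and 0.30. The share of lidocaine relief days in excess of placebo is then (0.50L − 0.30P) / 0.50L. L and P below are assumptions.

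| L (days) | P (days) | 0.50L | 0.30P | Share |
|---|---|---|---|---|
| 15 | 15 | 7.5 | 4.5 | 40% |
| 15 | 7 | 7.5 | 2.1 | 72% |
| 21 | 7 | 10.5 | 2.1 | 80% |
| 15 | 21 | 7.5 | 6.3 | 16% |

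The answer depends on P, which the documents do not give. The rates do not transfer either. They are for the composite endpoint (a 2-point fall in worst pain or an opioid reduction of at least 30%, lasting 7 days), whereas duration is the time for BPI question 3 to return to its starting value. A patient who responds only by reducing opioids, with pain unchanged, has no duration on this measure. A patient with a 1-point fall for 4 days has a positive one. The table shows only that the share is undetermined.

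**4. Which summary of the paired differences works?** Take 40 pairs on the plan's rates, with 15-day responses after either infusion (assumption): 12 respond to both (difference 0), 8 to lidocaine only (15) and 20 to neither (0). So 32 differences are zero.

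- Mean difference: 8 × 15 / 40 = 3.0 days.
- Hodges-Lehmann estimate: of 40 × 41 / 2 = 820 Walsh averages, 32 × 33 / 2 = 528 are zero, so the median is 0.

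With 15 days against 7, the differences are 20 zeros, 12 eights and 8 fifteens. The mean is (96 + 120) / 40 = 5.4 days. The Walsh averages include 210 zeros and 20 × 12 = 240 fours, so the median is 4. When many differences are zero, the mean is the more informative summary.

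**5. Who has a pair?** Between Visits arranges the second infusion only once worst pain has returned to baseline. Patients whose relief outlasts follow-up in the first period may never have a second duration, so an analysis restricted to pairs can lose the longest first-period responses. The plan's 20% drop-out allowance adds further losses.

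**The case against.** The strongest defence is that the label is loose but the definition is not. The measuring rule speaks of the infusion without naming a treatment, and the BPI schedule applies after each one. The primary outcome is also worded as something lidocaine caused, yet it is tested against placebo. Describing a secondary outcome without testing it is an open and legitimate choice. The stated use is conditional on the treatment being shown effective, and the primary endpoint already compares with placebo "a reduction in cancer pain within 48 hours of infusion and lasting a minimum of 7 days".

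Most of this stands. A reader might infer that relief which patients would also have had on placebo will be reported as lidocaine's effect. The documents do not support that: they are silent on tabulating placebo durations and do not forbid it.

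The defence does not supply the missing comparison. The primary test is binary at 7 days and cannot say how much longer relief lasts after lidocaine than after placebo. Nothing requires placebo durations to be reported, and an interval estimate of the difference is analysis that the plan currently excludes.

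**Conclusion.** The point holds as a worthwhile, low-cost improvement. Duration is named for lidocaine only, is excluded from statistical analysis, and has no planned comparison with placebo, although the blinded crossover collects what is needed. The primary endpoint, its power and its alpha are untouched.

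Its size cannot be stated. The assumed 30% placebo response is a reason to think that placebo relief may be appreciable, and no more. A reader might infer from the planning rates that 0.29995 / 0.50 = 60% of lidocaine responders would respond to placebo too, and that only 40% to 72% of relief days are due to lidocaine. The documents do not support carrying this over to duration: the rates describe a different response, the 60% rests on the 0.01% planning assumption, and the two percentages are chosen scenarios rather than bounds. Nor should 15 days per responder be set against 3.0 days per treated patient. On a common denominator of treated patients, the equal-duration example is 7.5 days after lidocaine and a 3.0-day difference.

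**What to change.** - Reword secondary objective and outcome 3 as duration of response after each infusion.
- For both treatments, summarise days until BPI question 3 returns to that infusion's pre-infusion value. Count patients without a reduction as 0. Truncate at Day 21, the last listed questionnaire day, or treat those not yet back at baseline as censored. Between Visits has responders continue weekly until return, so the choice should be stated.
- Report the mean within-patient difference (lidocaine minus placebo) with a 95% confidence interval from a bootstrap or permutation method. Do not rely on the Hodges-Lehmann estimate, because many differences will be zero.
- Include first-period durations of patients who never receive the second infusion in the by-treatment summaries and in a sensitivity analysis.
- Replace the sentence excluding duration from analysis with one saying that it is secondary, estimated with an interval, and carries no alpha.

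The cost is a few sentences and one extra analysis of data already collected, with no added patients, visits or forms. The sponsor should accept that the duration attributed to lidocaine may look less favourable.
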